## **1. SCIENTIFIC BACKGROUND**

Resistance training exercises are widely used to improve muscular strength and hypertrophy. Among these exercises, the bench press and machine chest press are commonly utilized for targeting the pectoralis major muscle. Although both exercises aim to activate similar muscle groups, differences in movement pattern, stabilization demand, and mechanical loading may result in distinct neuromuscular responses.

Muscle mechanical properties such as stiffness and tone can be objectively assessed using myotonometry. These parameters provide valuable information regarding muscle function, viscoelastic behavior, and acute responses to exercise. However, the extent to which different chest press variations influence these mechanical properties remains unclear.

Understanding the acute effects of these exercises on muscle mechanical characteristics may contribute to optimizing resistance training strategies and exercise selection.

## **2. OBJECTIVES AND HYPOTHESES**

### **2.1 Primary Objective**

To compare the acute effects of bench press and machine chest press exercises on pectoralis major muscle stiffness and tone.

### **2.2 Hypothesis**

It is hypothesized that different chest press variations will produce distinct acute changes in muscle mechanical properties, particularly stiffness and oscillation frequency.

## **3. STUDY DESIGN**

This study was designed as a randomized parallel-group experimental study. Participants were randomly assigned to either a bench press group or a machine chest press group.

All participants completed a single-session resistance exercise protocol. Muscle mechanical properties were assessed before and immediately after the exercise intervention.

The outcome assessor was blinded to group allocation.

## **4. PARTICIPANTS**

### **4.1 Study Population**

A total of 16 male resistance-trained athletes participated in the study.

#### **4.2 Inclusion Criteria**

- Male participants
- Aged between 20 and 40 years
- Minimum of 5 years of resistance training experience

#### **4.3 Exclusion Criteria**

- History of upper extremity injury within the last 12 months
- Previous upper extremity surgery
- Use of performance-enhancing substances

### **5. METHODS**

#### **5.1 Exercise Protocol**

Participants performed a standardized resistance training protocol consisting of four sets of ten repetitions at 80% of one-repetition maximum (1RM), with 2-minute rest intervals.

- Bench Press Group: Barbell bench press exercise
- Machine Chest Press Group: Machine chest press exercise

#### **5.2 Assessment of Muscle Mechanical Properties**

Muscle mechanical properties of the pectoralis major were assessed using MyotonPRO. Measurements were performed before and within 90 seconds after completion of the exercise protocol.

The following parameters were analyzed:

- Oscillation frequency (muscle tone)
- Stiffness
- Decrement
- Relaxation time
- Creep

### **6. OUTCOME MEASURES**

#### **Primary Outcomes**

- Change in muscle stiffness
- Change in oscillation frequency (muscle tone)

#### **Secondary Outcomes**

- Change in muscle decrement
- Change in relaxation time

- Change in creep

## **7. STATISTICAL ANALYSIS**

Data were analyzed using the SPSS 27.0 software package. The normality of the data distribution was assessed using the Shapiro-Wilk test; all parameters were found to exhibit a normal distribution ( $p > 0.05$ ). To examine the effect of exercise type on muscle mechanical properties, a Mixed-Design Analysis of Variance (ANOVA) was applied, where time (pre-test, post-test) was defined as a within-subject variable and group (BP, MCP) was defined as an between-subject variable. The primary focus of the analysis was the Time  $\times$  Group interaction effect, reflecting whether the two exercise protocols produced different changes in muscle mechanical properties from pre-test to post-test. For parameters where a significant Time  $\times$  Group interaction was detected, within-group pre-test–post-test differences were examined using a paired-samples t-test, and Bonferroni correction was applied for multiple comparisons. For ANOVA, effect sizes were reported as partial eta squared ( $\eta^2$ ) and interpreted as small ( $\eta^2 = 0.01$ ), moderate ( $\eta^2 = 0.06$ ), and large ( $\eta^2 \geq 0.14$ ) (Richardson, 2011). For within-group paired comparisons, effect sizes were calculated as Hedges'  $g$  and interpreted as small ( $< 0.35$ ), moderate ( $0.35\text{--}0.80$ ), and large ( $> 0.80$ ) (Rhea, 2004). The statistical significance level was set at  $p < 0.05$ .

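### The Time × Group test is a t-test on raw change: valid on average, but with 16 participants it leaves chance baseline imbalance unadjusted, which a baseline-adjusted analysis would correct at little cost

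*Protocol*

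**What the plan says.** Section 3 describes a randomised two-group study ("Participants were randomly assigned to either a bench press group or a machine chest press group"), and Section 5.2 gives one measurement on each side of the exercise: "Measurements were performed before and within 90 seconds after completion of the exercise protocol". Section 4.1 gives the size: "A total of 16 male resistance-trained athletes participated in the study". The allocation ratio is not stated.

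Section 6 defines the primary outcomes as changes, for example "Change in muscle stiffness", with oscillation frequency treated the same way. Section 7 fixes the model as a mixed-design ANOVA, "where time (pre-test, post-test) was defined as a within-subject variable", with group between subjects. Its main contrast is the interaction, "reflecting whether the two exercise protocols produced different changes in muscle mechanical properties from pre-test to post-test". Within-group follow-up tests are run only where that interaction is significant. No covariate is named. The protocol gives no SD, no pre/post correlation and no baseline values.

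**The concern.** The mixed ANOVA uses the pre-test as one level of the time factor, so it subtracts the baseline in full and does not adjust for it. If the true regression slope of post-test on pre-test is below 1, the group that starts higher by chance will tend to show the smaller change. In the sample drawn, that regression to the mean cannot be told apart from an effect of exercise type. With about eight men per group, moderate baseline differences are common.

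The interaction also decides which parameters get within-group follow-up, so a distorted interaction carries through to what is tested and reported next. The pre-test is already measured on everyone, so adjusting for it needs no new data.

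**Working it through.** **Inputs.** From the protocol: N = 16, two randomised groups, two time points, alpha 0.05. Assumed because the protocol does not give them: 8 per group; pre/post correlation rho from 0.3 to 0.9; ratio k of post-test SD to pre-test SD from 0.8 to 1.3. The protocol states no power or sample-size figure, so there is none to reproduce.

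**Step 1: what the interaction tests.** On simulated data with 8 per group, the interaction F(1,14) computed from sums of squares was 0.041563. The squared pooled t (14 df) on post minus pre was also 0.041563. The two tests are identical.

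**Step 2: how much imbalance to expect.** The SD of the baseline difference is sqrt(2/8) = 0.5 pre-test SD. A difference of at least 0.5 SD is therefore a 1-sigma event (32% of randomisations), and one of at least 1 SD a 2-sigma event (4.6%).

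**Step 3: effect of imbalance on the planned contrast.** In pre-test SD units the conditional bias is (k × rho − 1) × imbalance, which for equal SDs is (rho − 1) × imbalance. With rho 0.6 and imbalance 1 SD: (0.6 − 1) × 1 = −0.40 SD. Simulated type I error of the change-score test, given the imbalance (8 per group, equal SDs, rho 0.6):

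| Imbalance (SD) | Type I error |
|---|---|
| 0 | about 3% |
| 0.25 | 3.5% |
| 0.5 | 4.9% |
| 1 | about 11% |

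At 1 SD the error is about 8% for rho 0.8 and 6.4% for rho 0.9. ANCOVA has bias of about 0 and error of 5.0% at rho 0.6 and 1 SD. Averaged over all randomisations, both methods are unbiased with about 5% error.

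**Step 4: precision.** The large-sample variance ratio, ANCOVA to change score, is (1 − rho²)k² / (1 + k² − 2 × rho × k). For k = 1 this is (1 + rho)/2. At N = 16, estimating the slope multiplies it by 1 + 1/(16 − 4) = 13/12.

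- k = 1: break-even where (1 + rho)/2 × 13/12 = 1, so rho = 24/13 − 1 = 0.846.
- k = 1.3, rho 0.8: 0.6084/0.61 = 0.997. Times 13/12 this is 1.08, so ANCOVA is less precise.
- k = 0.8, rho 0.8: 0.2304/0.36 = 0.64. Times 13/12 this is 0.69, so ANCOVA is clearly more precise.

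Simulated ANCOVA power where the change-score test has 80% (true difference 1.507 SDs of the change):

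| rho | k = 1.0 | k = 1.2 | k = 1.3 |
|---|---|---|---|
| 0.3 | 91% | not quoted | not quoted |
| 0.5 | 87% | not quoted | 80% |
| 0.6 | 85% | 80% | 78% |
| 0.7 | 83% | 78% | 77% |
| 0.8 | 80% | 77% | 77% |
| 0.9 | 79% | 77% | about level |

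At k = 0.8 and rho 0.8 ANCOVA has about 92%. Mean 95% CI half-widths in pre-test SDs, change score against ANCOVA, are 1.05 against 0.95 (k = 1, rho 0.5), 0.47 against 0.48 (k = 1, rho 0.9) and 0.823 against 0.860 (k = 1.3, rho 0.8). The last is 0.860/0.823 = 1.045, or about 4.5% wider.

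**The case against.** The strongest reply is that nothing in Section 7 is wrong. The outcomes are defined as changes, the stated question is whether the changes differ, and under randomisation the change-score contrast answers it without bias and at the nominal level. A reader might infer from the 11% figure that the planned test has inflated type I error. It does not. That rate is conditional on an imbalance seen in fewer than 5% of randomisations, and for imbalances below 0.5 SD (about 68% of randomisations, at rho 0.6) the planned test is slightly conservative. This part of the reply stands.

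A reader might also infer that ANCOVA is always the more precise choice below a correlation of about 0.85. That break-even holds only for equal pre- and post-test SDs. If exercise increases the spread of the measurements, ANCOVA can lose a few points of power at ordinary correlations. The protocol gives neither the correlation nor the SD ratio, so no particular gain can be promised.

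Finally, Section 7 is written in the past tense and reports the outcome of the normality checks. If the data have already been compared by group, changing the primary test now would be a choice made after seeing results. That limits how the remedy may be presented.

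None of this removes the core point. The estimate still moves with baseline imbalance unless the slope is 1, and ANCOVA corrects for this by estimating the slope, whatever the SD ratio.

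**Conclusion.** The point holds as a limitation of a valid analysis, not as an error. The Time × Group test is exactly the t-test on raw change. With 16 participants it is exposed to chance imbalance: with 8 per group and equal SDs, the estimate shifts by (rho − 1) × imbalance, and type I error rises clearly above 5% only well beyond a 0.5 SD imbalance.

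The effect of adjustment on precision is uncertain. With equal SDs it ranges from a gain of about 11 power points (rho 0.3) to a loss of about 1 (rho 0.9). The gain is larger if the post-test SD is smaller. The loss reaches about 4 points, with an interval up to about 5% wider, if the post-test SD is 1.2 to 1.3 times the pre-test SD and rho is about 0.6 to 0.9. The documents do not show that a harmful imbalance occurred in this trial, since they give no baseline values.

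**What to change.** For each outcome, add an ANCOVA of the post-test value on group with the pre-test value of the same parameter as covariate. Report the adjusted group difference with its 95% CI beside the mixed-ANOVA interaction.

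If the outcomes have not yet been analysed by group, make the ANCOVA primary and the interaction supporting. If they have, label the ANCOVA as an added analysis and keep the planned interaction visible; do not replace it silently. The protocol should state which of the two applies.

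The cost is one or two sentences in Section 7, no new data, one error degree of freedom (14 to 13), and a possible small loss of precision when the slope of post-test on pre-test is near 1.

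### The follow-up tests and signed effect sizes are within-arm and depend on a significant interaction; the only between-exercise effect size is partial eta squared, which has no sign or units

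*Protocol*

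**What the plan says.** Section 2.1 states a between-exercise aim: "To compare the acute effects of bench press and machine chest press exercises on pectoralis major muscle stiffness and tone". Section 3 gives the design: "This study was designed as a randomized parallel-group experimental study". The primary outcomes in Section 6 are changes, the first being "Change in muscle stiffness".

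Section 7 uses a mixed ANOVA with time within subjects and group between subjects. It puts the main emphasis on the Time × Group interaction, described as "reflecting whether the two exercise protocols produced different changes in muscle mechanical properties from pre-test to post-test". Partial eta squared is the effect size for the ANOVA, with no condition on significance, and 0.14 or more counts as large.

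The next step changes the contrast. Only where the interaction is significant, the within-arm pre–post "differences were examined using a paired-samples t-test", with a Bonferroni correction. The remaining effect size belongs to those tests: "For within-group paired comparisons, effect sizes were calculated as" Hedges' g. Section 7 names no between-group difference in change, either in units or as a signed standardized value, and no confidence interval.

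**The concern.** With two groups and two time points, the interaction already is the comparison of the two mean changes. Once it is tested, the open questions are which exercise produced the larger change, by how much, and how precisely that is known. Paired tests within each arm answer a different question, namely whether that arm moved from its own baseline.

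Three consequences follow.

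- One arm can be significant and the other not when both have changed. A reader may then conclude that only one exercise alters stiffness or tone.
- Both arms exercise and neither rests, so a within-arm change cannot separate the exercise from re-measurement effects. The randomized difference between arms is not open to this problem in the same way, yet the follow-up tests and g are placed on the less protected contrast.
- A parameter whose interaction misses significance gets no signed estimate at all, however large its partial eta squared.

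**Working it through.** The protocol gives no power calculation, target effect or SD, so there is no figure of its own to reproduce.

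**Inputs.** Total N = 16 (Section 4.1). The split is not stated; I assume 8/8 and also check 7/9 and 6/10. Significance level 0.05 and the label of large at 0.14 (Section 7). Bonferroni is taken as two tests per parameter, so 0.025 per arm (assumed).

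**1. Interaction and change scores.** In a 2 × 2 mixed design the interaction F on (1, N − 2) df equals the square of the two-sample t on change scores. A simulated 8/8 data set confirmed this. Hence, with 14 df:

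- partial eta squared = F / (F + 14)
- |d| = √[F × (1/n₁ + 1/n₂)], in units of the SD of change

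So partial eta squared does convert to an unsigned between-exercise size. At 8/8, 0.01 gives |d| = 0.19, 0.06 gives 0.47, and 0.14 gives 0.75.

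**2. Where the follow-up starts.** The critical t on 14 df is 2.145, so critical F = 4.60.

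- Minimum partial eta squared = 4.60 / (4.60 + 14) = 0.247
- Minimum |d| at 8/8 = √(4.60 × 0.25) = 1.07

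**3. The plan's own large value.** At 0.14, F = (0.14 / 0.86) × 14 = 2.28, p = 0.15, |d| = 0.75, and the 95% CI for d is about −0.28 to 1.76. A parameter at this value is called large but gets no paired tests and no Hedges' g.

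**4. Precision of the between-group difference.** 95% CI half-width = 2.145 × √(1/n₁ + 1/n₂):

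| Split | Half-width (SD of change) |
|---|---|
| 8/8 | 1.07 |
| 7/9 | 1.08 |
| 6/10 | 1.11 |

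**5. What the within-arm tests show after a significant interaction.** Simulation of 400,000 trials per scenario: 8 per arm, changes in SD-of-change units, a one-sample t on 7 df at 0.025 in each arm, and a two-sample t on 14 df at 0.05 for the interaction. The true changes are assumed, because the protocol gives none.

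| True changes | True difference | Result among trials with a significant interaction |
|---|---|---|
| 0.5 and 1.3 | 0.8 | exactly one arm significant: 92% |
| 1.0 and 1.8 | 0.8 | exactly one arm significant: 64% |
| 1.5 and 2.3 | 0.8 | exactly one arm significant: about 20% |
| −0.4 and +0.4 | 0.8 | neither arm significant: 53% |

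The between-exercise difference is the same in every row, but the pattern of within-arm significance is not. The pattern therefore does not measure that difference. Power for the interaction at 0.8 SD is 32%, so the 92% corresponds to about 0.32 × 0.92 = 29% of all trials.

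**The case against.** The strongest reply is that the plan gets the main inference right. It tests the interaction first and uses paired tests only to describe a difference already shown. It therefore avoids the classic error of inferring a group difference from separate within-group tests, and nowhere does it claim that one exercise works and the other does not. This stands: the primary test is not at fault.

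A reader might go further and infer that no planned result gives the size of the difference between exercises. The document does not support that. Partial eta squared for the ANOVA is reported without a significance condition and can be converted to |d|. What it lacks is a sign, units and a stated interval.

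A reader might also infer that every estimate shown is selected on significance and so exaggerated. That does not hold either. Only the paired tests and the within-arm g depend on significance. Inflation factors for a between-group estimate would describe a quantity that the plan does not report.

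A statistical analysis plan that is not shown may add confidence intervals, so their absence is the weaker part of the point. It does not remove the core: the follow-up test, its condition and its effect size are fixed in Section 7 itself.

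Finally, the 92% depends on the scenario, which is why the range is given. The lack of a resting arm is a limit of the design and does not harm the comparative aim; it matters here only because the follow-up leans on within-arm change.

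**Conclusion.** The point holds as a mismatch between the objective and the follow-up. The interaction is the right primary test and partial eta squared gives its unsigned size. But the signed effect sizes and the follow-up tests are within-arm, appear only after a significant interaction, and do not estimate the between-exercise difference that Section 2.1 asks for.

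Two results do not rest on assumed effects. With N = 16 the follow-up needs partial eta squared of about 0.247, well above the plan's 0.14 for large, and this threshold is the same for any split. The 95% CI half-width for the difference in change is 1.07 to 1.11 SD over the splits checked, so a non-significant interaction would leave large differences open. The range of 92% to about 20% rests on assumed changes, an assumed 8/8 split and 0.025 per arm. It shows that the within-arm pattern can mislead, not how often it will in this trial.

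This should be changed. It does not invalidate the primary test.

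**What to change.** In Section 7, replace the conditional paired t-tests and within-arm Hedges' g with the following, for all five parameters and whatever the interaction p-value:

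- the between-group difference in mean change, in native units, with its 95% CI;
- a between-group Hedges' g, with its sign;
- within-arm mean changes with 95% CIs as description, without significance tests and without attributing them to the exercise.

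The interaction test and partial eta squared can stay as they are.

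The cost is a rewording of Section 7 and one extra output table. No new data are needed, and the power of the primary test is unchanged. Section 7 is written in the past tense, so if results have already been produced, the same quantities can be computed from the existing measurements and labelled as added to the plan.

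### With 16 participants, every significant Time × Group interaction is automatically labelled large on the protocol's partial eta squared scale, so the labels give no information about size

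*Protocol*

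**What the plan says.** Section 3 describes a parallel-group design: "Participants were randomly assigned to either a bench press group or a machine chest press group". Section 4.1 gives the size: "A total of 16 male resistance-trained athletes participated in the study".

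Section 7 specifies a mixed-design ANOVA in which "time (pre-test, post-test) was defined as a within-subject variable and group (BP, MCP) was defined as an between-subject variable". Its primary focus is the Time × Group interaction, described as "reflecting whether the two exercise protocols produced different changes in muscle mechanical properties from pre-test to post-test". The significance level is 0.05.

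On effect size, Section 7 says "For ANOVA, effect sizes were reported as partial eta squared" and attaches verbal labels: small at 0.01, moderate at 0.06, large at 0.14 or above. It states no small-sample correction for this index. The within-group follow-up is treated differently: "For within-group paired comparisons, effect sizes were calculated as Hedges" (that is, Hedges' g, which does carry a small-sample correction), with its own set of labels.

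**The concern.** The primary objective in Section 2.1 is a comparison between two exercises, and the interaction is the term that answers it. The label attached to that term is what many readers will take as the answer to how much the exercises differ.

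Partial eta squared is biased upward in small samples, and at fixed degrees of freedom it is a one-to-one function of the p-value. If the significance boundary lies well above the mark for large, the label cannot separate a modest effect from a big one among significant results. If chance alone often carries the index past the lower marks, the label also overstates non-significant results. At stake is how the size of the main comparison is described, not whether the test is correct.

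**Working it through.** **Inputs**
- Total N = 16 (Section 4.1), in two groups (Section 3). The split is not stated and is not needed for the main result.
- Two time points, one between-subject factor, focus on the interaction, significance level 0.05, marks at 0.01, 0.06 and 0.14 (all Section 7).
- The protocol states no figure of its own on this point, so there is none to reproduce first.

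**Step 1: degrees of freedom.** With two time points, the interaction F is the square of the two-sample t statistic on change scores. Its degrees of freedom are 1 and 16 − 2 = 14, for any split of 16.

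**Step 2: link between the index and F.** Partial eta squared = F / (F + 14).

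**Step 3: smallest significant value.** The critical value F(0.95; 1, 14) is 4.600. So the minimum is 4.600 / (4.600 + 14) = 4.600 / 18.600 = 0.247. This is above 0.14, so small and moderate can attach only to non-significant interactions.

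**Step 4: p-values at the marks.**

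| Partial eta squared | F = 14 × value / (1 − value) | p |
|---|---|---|
| 0.06 | 14 × 0.06 / 0.94 = 0.894 | 0.361 |
| 0.14 | 14 × 0.14 / 0.86 = 2.279 | 0.153 |

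**Step 5: behaviour with no true difference.** Under normality the index then follows a Beta(1/2, 7) distribution.
- Mean = 1 / (1 + 14) = 1/15 = 0.067.
- Median = 0.033.
- Chance of 0.06 or more = 36.1%.
- Chance of 0.14 or more = 15.3%.

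A simulation of 200,000 null trials at 8 v 8 gave a mean of 0.067, a median of 0.033, and 36.1% and 15.3%.

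**Step 6: behaviour with a true effect at the moderate mark.** Assume a population value of 0.06, so the noncentrality is 16 × 0.06 / 0.94 = 1.02. About 33% of trials would show 0.14 or more and be called large. About 16% would be significant, and all of those would be called large.

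**Step 7: sensitivity.**

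| Number analysed | Smallest significant value | Mean with no true difference |
|---|---|---|
| 16 | 0.247 | 1/15 = 0.067 |
| 15 | 0.264 | 1/14 = 0.071 |
| 14 | 0.283 | 1/13 = 0.077 |

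Losing participants makes it worse, and so does a stricter level (0.310 at 0.025 with 16 analysed). The automatic large label disappears only from a total N of about 28, where the minimum is 0.1398.

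**Step 8: would a corrected index cure it?** Values at the significance boundary with N = 16:
- Epsilon squared: 1 − (1 − 0.247) × 15/14 = 0.194 (unrounded input).
- Partial omega squared, change-score form: (4.600 − 1) / (4.600 − 1 + 16) = 3.600 / 19.600 = 0.184.
- Between-group Hedges' g, assuming 8 v 8: 2.145 × √(1/8 + 1/8) × (1 − 3/55) = 2.145 × 0.5 × 0.945 = 1.01.

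The first two still exceed 0.14. The third exceeds 0.80, the mark for large that Section 7 gives for within-group g and that is borrowed here only for comparison. Correction reduces the bias but does not rescue the labels.

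**The case against.** The strongest reply is that the labels decide nothing. Inference rests on the F test at 0.05, and the paired follow-up tests are triggered by a significant interaction, not by an eta squared label. That stands: the test and its p-value are unaffected, and this limits the severity.

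A second reply is that the cause is the small sample and not the choice of index, since any standardised between-group effect at fixed N is a function of the p-value. That also stands, as Step 8 shows. It means the remedy must be to drop the labels and report an interval; changing the index alone is not enough.

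A third is that Section 7 writes small and moderate as points and only large with an inequality, so treating 0.06 as a lower cut-off is a reading. It is a reasonable one, and the result for large does not depend on it.

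Four stronger readings are tempting but not supported:
- A reader might infer that a typical null result is called moderate. It is not. The mean of 0.067 only just passes 0.06, the distribution is skewed, the median is 0.033, and about 64% of null results fall below 0.06.
- A reader might infer that significant within-group g values are also always large. With 8 per group, a Bonferroni level of 0.025 and g scaled on the SD of change, the minimum would be (2.841 / √8) × 0.889 = 0.893. The protocol states none of those three inputs. If g used the raw-score SD, with equal SDs before and after, the minimum would be about 0.80, 0.69 or 0.56 at pre-post correlations of 0.6, 0.7 or 0.8. The last two are moderate on the protocol's scale.
- A reader might infer that no interval or between-group estimate is planned at all. A statistical analysis plan may supply these and is not at hand, so their absence is not itself the point.
- A reader might infer that a non-significant interaction will be reported as no difference. Section 7 does not say so.

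**Conclusion.** The point holds for the interaction labels. At 1 and 14 degrees of freedom, a rule stated in the protocol for its primary comparison calls every significant result large (minimum 0.247 against a mark of 0.14). It would also give 15% of results with no true difference that same label. The labels add nothing about size beyond the p-value, and they err upward.

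The significance boundary rests only on N = 16, two groups, two time points and the 0.05 level, all of which are stated. The null percentages also assume normally distributed change scores with equal variances in the two groups.

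Severity is moderate. It concerns reporting and interpretation, not the validity of the analysis.

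**What to change.** Remove the small, moderate and large labels for partial eta squared on the interaction in Section 7. For each primary outcome, report and interpret the between-group difference in pre-to-post change with its 95% confidence interval in measured units (for example N/m for stiffness and Hz for oscillation frequency; the protocol names no units).

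Omega squared, epsilon squared or a between-group Hedges' g, with a confidence interval, may be added to reduce the upward bias. They should carry no verbal labels, for the reason shown in Step 8.

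The cost is a change of wording and a few lines of output from data already collected. Section 7 is written in the past tense, so this may be a correction to the report instead of the plan. The downside is that effects will look less favourable and, with 16 participants, the intervals will be wide.
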